9.8 Serious Adverse Events

9.8.1 Definition of a Serious Adverse Event

A serious adverse event is an adverse event occurring at any dose that results in any of the following outcomes or actions:

- death
- a life-threatening adverse event (i.e., the patient was at immediate risk of death from the event as it occurred); does not include an event that, had it occurred in a more severe form, might have caused death

CONFIDENTIAL PROTOCOL

A Randomized, Double-Blind, Placebo-Controlled, Parallel Design, Multiple-Site Study to Evaluate the Therapeutic Equivalence of Estradiol Vaginal Cream USP, 0.01% (Teva Pharmaceuticals, USA) to Estrace® Estradiol Vaginal Cream, USP, 0.01% (Warner Chilcott) in the Treatment of Atrophic Vaginitis

- inpatient hospitalization or prolongation of existing hospitalization means that hospital inpatient admission and/or prolongation of hospital stay were required for treatment of an adverse event, or that they occurred as a consequence of the event. Hospitalizations scheduled for an elective procedure or for treatment of a pre-existing condition that has not worsened during participation in the study will not be considered serious adverse events.
- persistent or significant disability or incapacity (refers to a substantial disruption of one's ability to conduct normal life functions)
- a congenital anomaly/birth defect
- an important medical event that may not result in death, be life-threatening, or require hospitalization, but may jeopardize the patient and may require medical intervention to prevent one of the outcomes listed in this definition. Examples of such events are intensive treatment in an emergency room or at home for allergic bronchospasm; blood dyscrasias or convulsions that do not result in hospitalization; or the development of drug dependency or drug abuse. Note: Any suspected transmission of an infectious agent via a medicinal product is considered an important medical event.

An adverse event that does not meet any of the criteria for seriousness listed above will be regarded as a nonserious adverse event.

Expectedness

A serious adverse event that is not included in the Adverse Reaction section of the relevant reference safety information by its specificity, severity, outcome, or frequency is considered an unexpected adverse event. The reference safety information for this study is the ® Estrace® drug label.

The sponsor's Global Patient Safety & Pharmacovigilance Department will determine the expectedness for all serious adverse events.

9.8.2 Reporting Serious Adverse Events

It is the responsibility of the CRO to report a Serious Adverse Event (SAE) to the FDA within proper time constraints as per the Guidance for Industry and Investigators Safety Reporting Requirements for INDs and BA/BE Studies.¹⁹ Confirmation of this report must then be provided to Teva's study representative as well as their Pharmacovigilance department (contact information below).

Any serious adverse event (SAE) that occurs after the start of the study period must be reported by the study site, in English, within 24 hours of becoming aware of the SAE, to the study representative at [REDACTED] as well as one of the contacts listed below. All serious adverse events occurring during the study period, whether or not considered to be related to the study drug, must be reported within 24 hours to the study representative at [REDACTED] as well as the two contacts below.:

CONFIDENTIAL PROTOCOL

A Randomized, Double-Blind, Placebo-Controlled, Parallel Design, Multiple-Site Study to Evaluate the Therapeutic Equivalence of Estradiol Vaginal Cream USP, 0.01% (Teva Pharmaceuticals, USA) to Estrace® Estradiol Vaginal Cream, USP, 0.01% (Warner Chilcott) in the Treatment of Atrophic Vaginitis

Or

[REDACTED] will be responsible for reporting the SAE to Teva using the following guidelines.

PLEASE NOTE THAT EMAIL IS THE PREFERRED MEANS OF COMMUNICATION.

[REDACTED]
Teva Pharmaceuticals USA
[REDACTED]

AND

Teva Pharmacovigilance
[REDACTED]

These SAE reports must contain the following information:

- Study name/number (for EU also the EudraCT number)
- Study Drug
- Investigator details (name, phone, fax, e-mail)
- Patient Number
- Patient Initials
- Patient Demographics
- Clinical Event
 - Description
 - Date of onset
 - Treatment (drug, dose, dosage form)
 - AE Relationship to study drug
 - Action taken regarding study drug in direct relationship to the AE

CONFIDENTIAL PROTOCOL

A Randomized, Double-Blind, Placebo-Controlled, Parallel Design, Multiple-Site Study to Evaluate the Therapeutic Equivalence of Estradiol Vaginal Cream USP, 0.01% (Teva Pharmaceuticals, USA) to Estrace® Estradiol Vaginal Cream, USP, 0.01% (Warner Chilcott) in the Treatment of Atrophic Vaginitis

Additional information may include the following:

- date of first dose of study drug
- date and amount of last administered dose of study drug
- action taken
- outcome, if known
- severity
- concomitant therapy (including doses, routes, and regimens) and treatment of the event
- pertinent laboratory or other diagnostic test data
- medical history
- results of dechallenge/rechallenge, if known
- for an adverse event resulting in death:
- cause of death (whether or not the death was related to study drug)
- autopsy findings (if available)

For the purposes of SAE reporting, the study period is defined as the time period from the first dose through the follow-up period. For this study, the follow-up period is defined as 30 days after the last study visit. All SAEs occurring during the study period, whether or not considered to be related to the study drug, must be reported within 24 hours to the study representative at [REDACTED] as well as the two contacts above. [REDACTED] will report the SAE to Teva. Even though the investigator does not need to actively monitor patients for adverse events once the study has ended, serious adverse events occurring to a patient after their treatment has ended should be reported to [REDACTED] if the investigator becomes aware of them.

[REDACTED] will be responsible for notifying the Investigative sites as required. Under 21 CFR 320.31 (d)(3) the Investigator must inform other investigators involved in the study plus the FDA within 15 days of becoming aware of the occurrence of the serious AEs. Serious AEs that occur with the study drugs must be reported.¹⁹

10.0 STATISTICAL METHODS

10.1 Statistical Plan

A Statistical Analysis Plan (SAP) including study data report format, following FDA guidance “Draft Guidance on Estradiol Cream 0.01% revised Sept 2014) detailing the intended statistical analysis of the study data, will be prepared as a separate document and finalized before database lock. Any deviation from the original statistical plan will be

CONFIDENTIAL PROTOCOL

A Randomized, Double-Blind, Placebo-Controlled, Parallel Design, Multiple-Site Study to Evaluate the Therapeutic Equivalence of Estradiol Vaginal Cream USP, 0.01% (Teva Pharmaceuticals, USA) to Estrace[®] Estradiol Vaginal Cream, USP, 0.01% (Warner Chilcott) in the Treatment of Atrophic Vaginitis

described and justified in the final report, as appropriate. The procedure for accounting for missing, unused and spurious data will be included in the Statistical Analysis Plan.

All statistical analysis will be conducted using SAS[®], Version 9.4 or higher.

10.2 Determination of Sample Size

The primary statistical analysis of interest is the proportion of patients in the Per Protocol (PP) population that are identified as “Responders” at the end of the treatment period evaluated on Day 8 + 1.

sample size of 224 patients

a

Using a 2:1 (active: placebo) randomization scheme, and assuming the conversion rate from mITT to PP will be about 90%, 250 patients in each of active groups and 125 patients in the placebo group of the mITT population

To allow for about 5% of patients who may drop out from the study or are otherwise non-evaluable, up to 660 patients may be randomized to obtain 625 patients in the mITT population (i.e., 250 in each active group and 125 in the Placebo group).

10.3 Study Populations

10.3.1 Per-Protocol Population

Patients will be eligible for inclusion in the PP population if they:

- Met the inclusion/exclusion criteria as defined in this protocol at Visit 1 and 2
- Did not take any prohibited medications throughout the study
- Did not have any significant deviations from the protocol
- Did not develop any concurrent vaginal infection or illness exhibiting symptoms similar to atrophic vaginitis, or symptoms that in the Investigator’s opinion would interfere with primary and secondary endpoint assessments

CONFIDENTIAL PROTOCOL

A Randomized, Double-Blind, Placebo-Controlled, Parallel Design, Multiple-Site Study to Evaluate the Therapeutic Equivalence of Estradiol Vaginal Cream USP, 0.01% (Teva Pharmaceuticals, USA) to Estrace® Estradiol Vaginal Cream, USP, 0.01% (Warner Chilcott) in the Treatment of Atrophic Vaginitis

- Completed the last study visit (Visit 3) Day 8 + 1.
- Were compliant with dosing between 75%-125% of the required doses (6 – 8 doses), and did not miss more than 1 dose
- Any patient who withdrew from the study because of lack of efficacy will be included in the PP population as a Non-Responder. Patients who discontinue early for other reasons should be excluded from the PP population and included in the mITT population using Last Observation Carried Forward (LOCF).

10.3.2 mITT Population

The mITT population will include all patients in the PP population, AND patients who:

- Administered at least one dose of randomized study medication and
- Had a post-randomization evaluation

10.3.3 Safety Population

The safety population will include all patients who are randomized and administered at least one dose of study drug.

10.4 Baseline Comparability

Baseline comparability of all treatment groups will be evaluated separately in the PP, mITT and Safety populations. The following baseline demographics (determined from their initial study visit) will be evaluated:

- Age (years)
- Gender (male/female)
- Ethnicity (Hispanic/non Hispanic)
- Race (White, Black/African American, Native Hawaiian or Other Pacific Islander, Asian, American Indian or Alaska Native, Other)
- natural or surgical menopause
- duration of postmenopausal status
- baseline signs and symptoms
- baseline % of the three major vaginal wall cell types (basal/parabasal cells, intermediate cells and superficial cells)
- vaginal pH

Descriptive statistics by treatment group will be presented.

CONFIDENTIAL PROTOCOL

A Randomized, Double-Blind, Placebo-Controlled, Parallel Design, Multiple-Site Study to Evaluate the Therapeutic Equivalence of Estradiol Vaginal Cream USP, 0.01% (Teva Pharmaceuticals, USA) to Estrace[®] Estradiol Vaginal Cream, USP, 0.01% (Warner Chilcott) in the Treatment of Atrophic Vaginitis

10.5 Efficacy Endpoints

Primary Efficacy Endpoint

The primary efficacy endpoint is the proportion of patients in the PP population that are identified as “Responders” at the end of the treatment period evaluated on Day 8 + 1.

A responder is defined as a patient with at least a 25% reduction from baseline in the sum of % basal/parabasal + % intermediate cells on vaginal cytology AND vaginal pH < 5.0 with a change from baseline vaginal pH of at least 0.5.

Secondary Efficacy Endpoint

The secondary efficacy endpoint is the proportion of patients in the PP population that are identified as “Treatment Success” at the end of the treatment period evaluated on Day 8 + 1.

A “Treatment Success” is defined as a score of 0 or 1 at Day 8 + 1 for the symptom identified at baseline as the most bothersome. This evaluation is to be based on patient self-assessed symptoms of vulvar and vaginal atrophy on a scale of 0 to 3 where 0 = none and 3 = severe. Refer to Appendix B for rating scales.

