3	Severe	Vaginal penetration very painful and impossible without vaginal lubrication. Discomfort such that frequency of sexual activity significantly reduced.

Vaginal bleeding during or after sexual activity		
Score	Severity	Description
0	Absent	No vaginal bleeding observed
1	Present	Bleeding observed during or soon after vaginal activity

At each visit each patient must also clearly identify which is the most bothersome sign/symptom to her, even if she rates two or more symptoms the same severity rating.

CONFIDENTIAL PROTOCOL

A Randomized, Double-Blind, Placebo-Controlled, Parallel Design, Multiple-Site Study to Evaluate the Therapeutic Equivalence of Estradiol Vaginal Cream USP, 0.01% (Teva Pharmaceuticals, USA) to Estrace® Estradiol Vaginal Cream, USP, 0.01% (Warner Chilcott) in the Treatment of Atrophic Vaginitis

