7. STUDY ENDPOINTS

Primary Efficacy Endpoint

Estradiol Vaginal Cream USP, 0.01%

Protocol/Study Number 71436001

The primary efficacy endpoint is the proportion of patients in the PP population that are identified as "Responders" at the end of the treatment period evaluated on Day 8 ± 1 .

A responder is defined as a patient with at least a 25% reduction from baseline in the sum of % basal/parabasal + % intermediate cells on vaginal cytology AND vaginal pH < 5.0 with a change from baseline vaginal pH of at least 0.5.

Secondary Efficacy Endpoint

The secondary efficacy endpoint is the proportion of patients in the PP population that are identified as "Treatment Success" at the end of the treatment period evaluated on Day 8 ± 1 .

A "Treatment Success" is defined as a score of 0 or 1 at Day 8 ± 1 for the symptom identified at baseline as the most bothersome. This evaluation is to be based on patient self-assessed symptoms of vulvar and vaginal atrophy on a scale of 0 to 3 where 0 = none and 3 = severe.

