8.2 Efficacy Analyses

The following symptoms (see Appendix A for detailed rating scales) will be evaluated at Visits 1, 2 and 3 by the blinded clinical staff or Investigator.

Symptoms	Rating Scales
Vaginal Dryness	0=None, 1=mild, 2=moderate, 3=severe
Vaginal/Vulvar irritation/itching	0=None, 1=mild, 2=moderate, 3=severe
Dysuria	0=None, 1=mild, 2=moderate, 3=severe
Vaginal Pain associated with Sexual Activity	0=None, 1=mild, 2=moderate, 3=severe
Vaginal Bleeding	0= Absent, 1= Present

The patients will be asked to identify which symptom is considered to be the most bothersome symptom at Visit 1 and Visit 2. Vaginal Pain associated with Sexual Activity or Vaginal

Estradiol Vaginal Cream USP, 0.01%

Protocol/Study Number 71436001

Bleeding are acceptable to be considered most bothersome symptom only if patient is currently sexually active and plans to remain so throughout the study.

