8.2.2 Analysis of Secondary Efficacy Endpoint

Therapeutic Bioequivalence Analysis

Similar to the analysis for primary endpoint above, therapeutic equivalence of the Test product to the Reference product based on the secondary endpoint will be evaluated in the PP population after the end of treatment on Day 8 ± 1 .

Secondary analysis will compare the proportion of patients considered to be a "Treatment Success" for their most bothersome symptom. A "Treatment Success" is defined as a score of 0 or 1 at Day 8 for the symptom identified at baseline as the most bothersome). If the 90% confidence interval (calculated using Yates' continuity correction) for the absolute difference between the proportion of patients considered as "Treatment Success" in the Test and Reference groups is contained within the range [-20%, +20%] then bioequivalence of the Test product to the Reference product will be considered to have been demonstrated for the secondary endpoint.

To declare therapeutic equivalence of the Test product to the Reference product, bioequivalence

Estradiol Vaginal Cream USP, 0.01%

Protocol/Study Number 71436001

must be demonstrated for only the primary endpoint. Bioequivalence testing of the secondary endpoint will be conducted for supportive information.

Superiority to Placebo Analysis

The mITT population and LOCF will be used to evaluate the superiority of both the Test and Reference product to Placebo.

Similar to the analysis for primary endpoint above, superiority of the Test and Reference products against the Placebo for secondary endpoints will be tested at the 5% significance level (p < 0.05; using two-sided, continuity-corrected Z-test) in the mITT population using last observation carried forward. The superiority of Test and Reference treatments over the Placebo will be evaluated identically in separate Z-Test analyses.

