Vaginal Dryness	None	xxx (xx.x%)	xxx (xx.x%)	xxx (xx.x%)	x.xxxx
	Mild	xxx (xx.x%)	xxx (xx.x%)	xxx (xx.x%)	
	Moderate	xxx (xx.x%)	xxx (xx.x%)	xxx (xx.x%)	
	Severe	xxx (xx.x%)	xxx (xx.x%)	xxx (xx.x%)	
Vaginal/Vulvar Irritation/Itching	None	xxx (xx.x%)	xxx (xx.x%)	xxx (xx.x%)	x.xxxx
	Mild	xxx (xx.x%)	xxx (xx.x%)	xxx (xx.x%)	
	Moderate	xxx (xx.x%)	xxx (xx.x%)	xxx (xx.x%)	
	Severe	xxx (xx.x%)	xxx (xx.x%)	xxx (xx.x%)	

Test: Estradiol Vaginal Cream, USP, 0.01% (Teva Pharmaceuticals, USA)

Reference: Estrace® Cream (estradiol vaginal cream, USP, 0.01%; Warner Chilcott)

Placebo: Placebo cream (Teva Pharmaceuticals, USA)

Path: L:\Studies_Sas_Codes\Clinical Trial\71436001\PDF\xxx

Created on: ddmmmyy hh:mm

T16.1.9.4 Summary of Baseline Demographic Data (Safety Population)

		Test	Reference	Placebo	P-value
		$(\mathbf{N} = \mathbf{x}\mathbf{x}\mathbf{x})$	$(\mathbf{N} = \mathbf{x}\mathbf{x}\mathbf{x})$	$(\mathbf{N} = \mathbf{x}\mathbf{x}\mathbf{x})$	
Dysuria	None	xxx (xx.x%)	xxx (xx.x%)	xxx (xx.x%)	X.XXXX
	Mild	xxx (xx.x%)	xxx (xx.x%)	xxx (xx.x%)	
	Moderate	xxx (xx.x%)	xxx (xx.x%)	xxx (xx.x%)	
	Severe	xxx (xx.x%)	xxx (xx.x%)	xxx (xx.x%)	
Vaginal Pain during Sexual Activity	None	xxx (xx.x%)	xxx (xx.x%)	xxx (xx.x%)	x.xxxx
	Mild	xxx (xx.x%)	xxx (xx.x%)	xxx (xx.x%)	
	Moderate	xxx (xx.x%)	xxx (xx.x%)	xxx (xx.x%)	
	Severe	xxx (xx.x%)	xxx (xx.x%)	xxx (xx.x%)	
Most Bothersome Sign or Symptom	Vaginal Dryness	xxx (xx.x%)	xxx (xx.x%)	xxx (xx.x%)	x.xxxx
	Vaginal/Vulvar Irritation/Itching	xxx (xx.x%)	xxx (xx.x%)	xxx (xx.x%)	
	Dysuria	xxx (xx.x%)	xxx (xx.x%)	xxx (xx.x%)	
	Vaginal Pain during Sexual Activity	xxx (xx.x%)	xxx (xx.x%)	xxx (xx.x%)	
	Vaginal Bleeding	xxx (xx.x%)	xxx (xx.x%)	xxx (xx.x%)	

Test: Estradiol Vaginal Cream, USP, 0.01% (Teva Pharmaceuticals, USA)

Reference: Estrace® Cream (estradiol vaginal cream, USP, 0.01%; Warner Chilcott)

Placebo: Placebo cream (Teva Pharmaceuticals, USA)

Created on: ddmmmyy hh:mm

T16.1.9.4 Summary of Baseline Demographic Data (Safety Population)

		Test	Reference	Placebo	P-value
		(N = xxx)	(N = xxx)	$(\mathbf{N} = \mathbf{x}\mathbf{x}\mathbf{x})$	
Vaginal Bleeding	Absent	xxx (xx.x%)	xxx (xx.x%)	xxx (xx.x%)	x.xxxx
	Present	xxx (xx.x%)	xxx (xx.x%)	xxx (xx.x%)	
Duration of Postmenopausal Status (Years)	XXX	XXX	xxx	xxx	
	$xx.x \pm xx.xx$	$xx.x \pm xx.xx$	$xx.x \pm xx.xx$	$xx.x \pm xx.xx$	x.xxxx
	XX.X	XX.X	XX.X	XX.X	
	xx.x - xx.x	xx.x - xx.x	xx.x - xx.x	xx.x - xx.x	
% of basal/parabasal cells	XXX	XXX	XXX	XXX	

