3	Severe	Vaginal penetration very painful and impossible without vaginal lubrication. Discomfort such that frequency of sexual activity significantly reduced.			

Vaginal bleeding during or after sexual activity				
Score	Severity	Description		
0	Absent	No vaginal bleeding observed		
1	Present	Bleeding observed during or soon after vaginal activity		

At each visit each patient must also clearly identify which is the most bothersome sign/symptom to her, even if she rates two or more symptoms the same severity rating.

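### Secondary Treatment Success (score 0 or 1) cannot fail when the most bothersome symptom is vaginal bleeding, because bleeding is scored only 0 or 1

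*Protocol*

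**What the plan says.** Protocol 10.5 gives the secondary endpoint, Treatment Success, which "is defined as a score of 0 or 1 at Day 8 + 1 for the symptom identified at baseline as the most bothersome". The same paragraph describes a 0-to-3 patient-rated scale and points to Appendix B for the ratings. SAP 7 uses the same rule ("is defined as a score of 0 or 1 at Day 8 ± 1 for the symptom identified at baseline as the most bothersome"), as does SAP 8.2.2 ("is defined as a score of 0 or 1 at Day 8 for the symptom identified at baseline as the most bothersome").

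Four of the five symptoms are graded 0 to 3. Vaginal bleeding is not: SAP 8.2 gives "0= Absent, 1= Present". In Protocol Appendix B score 1 means "Bleeding observed during or soon after vaginal activity", and in SAP Appendix A score 0 means "No vaginal bleeding observed".

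Bleeding can be the most bothersome symptom. It is item 5e of the inclusion criteria (Protocol 9.3.1). SAP 8.2 says that pain with sexual activity or vaginal "Bleeding are acceptable to be considered most bothersome symptom only if patient is currently sexually active and plans to remain so throughout the study". Shell T16.1.9.4 has a row for it under "Most Bothersome Sign or Symptom".

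Inclusion criterion 5 also asks for a symptom of moderate to severe intensity, which a present/absent item cannot express.

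**The concern.** The threshold of 0 or 1 suits a four-grade scale, where it separates none or mild from moderate or severe. On the bleeding item it covers every possible score. A woman whose most bothersome symptom is bleeding meets the success criterion before her first dose and cannot stop meeting it, so the endpoint carries no information about her.

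The endpoint is formally analysed. Protocol 10.7 and SAP 8.2.2 test Test and Reference against Placebo on it at the two-sided 5% level, and Protocol 10.6 applies the ±20-point equivalence range to it. Automatic successes in every arm would tend to pull differences toward zero, which helps equivalence and works against superiority.

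The stakes are limited. Equivalence is declared on the primary endpoint alone, and SAP 8.2.1 confirms study sensitivity from Responders alone.

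**Working it through.** **1. Applying the rule to each possible score.** This step needs no assumed figure.

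| Baseline most bothersome symptom | Possible Visit 3 scores | Successes under the rule |
|---|---|---|
| Dryness, irritation/itching, dysuria, pain with sexual activity | 0, 1, 2, 3 | 0 and 1 |
| Vaginal bleeding | 0, 1 | 0 and 1, that is, all |

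**2. Inputs for size.** From the documents: 224 per active arm in the PP set; 250 per active arm and 125 on placebo in the mITT set (total 625); the Yates-corrected 90% CI of SAP 8.2.1; a two-sided 5% continuity-corrected Z-test. The documents do not give f, the share with bleeding as most bothersome symptom, or any success rate for this endpoint, so there is no figure in the plan to reproduce. I assume f equal across arms and show 0 to 10%. The SAP gives no variance formula for the Z-test; pooled variance is assumed.

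**3. Effect on the rates.** Let p be an arm's success rate under a rule that works for every symptom, assumed the same in bleeding and other patients. As written, the arm rate becomes p' = f + (1-f)p, so a difference d becomes (1-f)d. At f = 5%:
- 40% v 60% becomes 0.05 + 0.95 × 0.40 = 43.0% v 0.05 + 0.95 × 0.60 = 62.0%; the difference goes from 20 to 19 points.
- 50% v 35% becomes 52.5% v 38.25%; the difference goes from 15 to 14.25 points.

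**4. Effect on the decisions.** These are exact binomial enumerations. The equivalence column takes true rates of 40% v 60%, at the edge of the range, with 224 per arm. The superiority column takes 50% v 35% with 250 v 125.

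| f | Women among 625 (625f) | Passes equivalence | Superiority power |
|---|---|---|---|
| 0 | 0 | 3.9% | 75.5% |
| 1% | about 6 | 4.3% | 74.5% |
| 2% | about 13 | 4.7% | 73.4% |
| 5% | about 31 | 6.1% | 70.3% |
| 10% | about 63 | 9.1% | 65.2% |

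The equivalence case is a boundary case, because the SAP's alternative hypothesis includes a difference of exactly -0.20.

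**5. The other extreme.** Suppose bleeding patients show no between-arm difference, with 70% success in every arm under a corrected rule. The corrected arm rate is 0.7f + (1-f)p, so the difference is (1-f)d both before and after the correction.

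| f | Power, as written | Power, corrected | Passes equivalence, as written | Passes equivalence, corrected |
|---|---|---|---|---|
| 5% | 70.3% | 70.55% | 6.13% | 6.15% |
| 10% | 65.2% | 65.4% | 9.1% | 9.2% |

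Here the correction changes who counts as a success and almost nothing else.

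**The case against.** The best counter-argument is that the rule is undefined for bleeding rather than wrong. The definition speaks of a 0-to-3 scale, which bleeding does not use, and a strict reading of moderate to severe in criterion 5 would keep bleeding from qualifying, making f zero. This does not stand. The same paragraph sends the reader to Appendix B, where bleeding is 0/1. Item 5e, SAP 8.2 and T16.1.9.4 all admit bleeding. A programmer following the text would code score 1 as a success. The moderate to severe wording is a further contradiction, not a safeguard.

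Several points about size do stand:
- The group is probably narrow. Bleeding must be the single most bothersome of five symptoms in a sexually active woman, and exclusions 13 and 16 remove undiagnosed bleeding and genital bleeding of unknown cause. Nothing in the documents supports f of 5% or 10%. At 1 to 2% the shifts are 0.4 to 0.8 points in equivalence pass rate and 1.1 to 2.1 points in power.
- The pull toward zero that a correction would remove depends on a same-direction effect in bleeding patients and on equal f across arms. With unequal f the bias could go either way.
- Patients who withdraw for lack of efficacy enter the PP set as Non-Responders. That term belongs to the primary endpoint and its bearing on Treatment Success is unstated, but it could make an exception for a few women.
- No stated conclusion depends on the secondary endpoint, so it could be called a minor clarification. But it is a planned 5%-level test, and counting a persistent symptom as a success is an error whatever its frequency.

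**Conclusion.** The concern holds. As written, a woman whose baseline most bothersome symptom is vaginal bleeding and who has a bleeding score, recorded or carried forward, is a Treatment Success whether or not the bleeding has stopped. That follows from the definitions alone.

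The numerical effect is conditional on f, on equal f across arms, on the assumed success rates and on how bleeding patients would respond. It is small at f of 1 to 2%, and reaches about 5 points of superiority power at f = 5% and 10 points at f = 10% if the treatment effect is the same in all patients. If bleeding patients show no between-arm difference, the benefit of a correction is better classification only. The primary endpoint, the equivalence declaration and the confirmation of sensitivity are unaffected. The change should be made, but the main conclusion does not depend on it.

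**What to change.** Before unblinding, amend Protocol 10.5/10.6 and SAP 7/8.2.2 so that success is a score of 0 or 1 for the four symptoms graded 0 to 3, and a score of 0 (absent) when the baseline most bothersome symptom is vaginal bleeding. Program L16.2.6.2 and T16.1.9.8 to match, and report the number of such women per arm. Reconcile the moderate to severe wording of inclusion criterion 5 with the present/absent bleeding item.

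The cost is one sentence in each document and one line of code, with no new data, since the bleeding score is already collected at Visit 3. Success rates will fall in all arms, by f(1-p) in the same-effect case. With 50% active and 35% placebo success, that is 0.5 and 0.65 points at f = 1%, 2.5 and 3.25 at 5%, and 5.0 and 6.5 at 10%. In the no-effect case at 70% they fall by 0.3f in every arm.

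One limit remains: the item records bleeding with sexual activity, so a woman with no activity during treatment could still score 0. The correction improves classification without making it perfect.
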